2	02/24/2016	
Added updated DSMC language as requested by the MCW DSMC on 1/22/15:
 
This study will be reviewed by the Medical College of Wisconsin Cancer Center Data and Safety Monitoring Committee (MCWCC DSMC). A summary of the MCWCC DSMC activities are as follows:
 
 • Review the clinical trial for data integrity and safety. • Review all unexpected grade 3, and all grade 4, and 5 adverse events, as well as any others requiring expedited reporting as defined in this protocol. (Grades 4 & 5 events must be reported to the DSMC within 5 calendar days of study staff’s knowledge.) • Review all DSM reports. • Submit a summary of any recommendations related to study conduct. • Terminate the study if deemed unsafe for patients. 
A copy of the MCWCC Data and Safety Monitoring Plan and membership roster will be maintained in the study research file and updated as membership changes. The committee will review reports from the study PI twice annually (or more frequently if needed) and provide recommendations on trial continuation, suspension or termination as necessary. Any available DSMC letters will be submitted to the IRB of record as required.
	
YES –
 
Footers/Headers only– updated to protocol v2 Dated 2/24/2016
 
 • Consent Spanish Short Form • HIPAA Adult • HIPAA Adult Spanish • HIPAA Child • HIPAA Child Spanish

SYNOPSIS

Study Title: A Randomized Controlled Trial Investigating Topical Caphosol for Prevention of Oral Mucositis in Children, Adolescents and Young Adults (AYA) Receiving Chemotherapy

Randomized Controlled Trial

[figure not shown]
Number of Patients: A total of 96 patients will enroll to this study with 48 patients in the Caphosol group and 48 patients in the control group.

Study Objectives

- **Primary Objectives**
 - To determine if topically administered Caphosol at the initiation of chemotherapy prevents the development of oral mucositis (Grade ≥ 2) in children, adolescents and young adults.
 - To determine the tolerability of four times daily Caphosol therapy.

- **Secondary Objectives**
 - To determine if topically administered Caphosol reduces the severity of oral mucositis, as measured by incidence of severe mucositis (CTCAE v4.0 Grades 3 or 4), age-appropriate pain scores (FACES and Likert), use of narcotic pain medicine, number of hospital days and duration of total parenteral nutrition (TPN).

Treatment Plan Schema

Caphosol Administration:

- Take 30 mL QID (can increase frequency up to 6 times daily with symptoms of mucositis).
- Each dose consists of 2, 15 mL syringes, to be mixed at time of administration. Caphosol must be used within 15 minutes of mixing.
- Rinse and gargle (if patient is able) approximately half of the solution (15 mL) for one minute and then spit. Repeat.
- For younger patients (≤ 6 years of age), volume may be reduced to 10-20 mL (5-10 mL x 2).
- For patients unable to successfully rinse and spit, caregivers may paint their mouth (using medical sponge swabs) with the solution x 2. Prior to swabbing the patient's mouth, mix half of the 2, 15 mL syringes into a cup and dip swab prior to coating the inside of the patient's mouth. Repeat
- Patients are to avoid other oral medications, other mouth cares and food or drink for 15 minutes after using Caphosol.
- Take Biotene (5-10 mL) QID swish and spit

Control Arm:

- Take Biotene (5-10 mL) QID swish and spit
- For patients unable to successfully rinse and spit, caregivers may paint their mouth (using medical sponge swabs) with the solution x 2. Prior to swabbing the patient's mouth, mix 5-10 mL into a cup and dip swab prior to coating the inside of the patient's mouth. Repeat

Study Population:

- Oncology patients at any point during their oncology therapy who are at risk of developing oral mucositis defined as:
 - Patients receiving one or more of the following chemotherapy agents associated with high incidence of oral mucositis:
 - Actinomycin D
 - Carboplatin
 - Cisplatin
 - Cytarabine at doses ≥ 1 gram/m²
 - Daunorubicin
 - Doxorubicin
 - Methotrexate at doses > 1 gram/m²
 - Mitoxantrone
- Age 0 to 25 years.
- Voluntary written consent before performance of any study-related procedure not part of normal medical care, with the understanding that consent may be withdrawn by the subject at any time without prejudice to future medical care.

Exclusion Criteria:

- Patients receiving glutamine therapy for mucositis.
- Patients receiving concurrent Head & Neck radiation therapy or within 6 weeks of completion of radiation therapy.
- Patients receiving autologous or allogeneic hematopoietic cell transplantation
- Pregnant or lactating patients. The agent used in this study is not known to be teratogenic to a fetus, but has not been studied, and there is no information on the excretion of the agent into breast milk. All females of childbearing potential must have a blood test or urine study within 2 weeks prior to registration to rule out pregnancy.
- Known allergy to Caphosol.

Duration of Study: 6-8 months

1.0 BACKGROUND

Mucositis in Children, Adolescents and Young Adults Undergoing Chemotherapy

Oral mucositis, a common and debilitating complication of cancer therapy, is an inflammatory injury to the epithelial and sub-epithelial cells of the oral mucosa. Oral mucositis is thought to develop according to a five-stage model: 1) initiation; 2) up-regulation with generation of messengers; 3) signaling and amplification 4) ulceration with inflammation; and 5) healing, and typically develops 7-14 days into a chemotherapy course (1).

The incidence and severity of oral mucositis depends on many factors including the age and diagnosis of the patient, the specific treatment regimen, underlying oral hygiene and genetic factors (2-4). The incidence of oral mucositis in patients receiving chemotherapy ranges from around 40% of patients receiving myelosuppressive chemotherapy for solid tumors to 70-90% of patients receiving myeloablative therapy prior to stem cell transplant (1, 5, 6). A commonly used grading scale for mucositis is the Common Terminology Criteria for Adverse Events (CTCAE version 4.0) grading scale, where grading is based on both subjective and objective assessments on a 5 point scale (Grade 1 to Grade 5).

Adverse Event	1	2	3	4	5
Mucositis Oral Definition: A disorder characterized by inflammation of the oral mucosal.	Asymptomatic or mild symptoms; intervention not indicated	Moderate pain; not interfering with oral intake; modified diet indicated	Severe pain; interfering with oral intake	Life-threatening consequences; urgent intervention indicated	Death

From the Common Terminology Criteria for Adverse Events (CTCAE) Version 4.0 Published: May 28, 2009 (v4.03: June 14, 2010) U.S. DEPARTMENT OF HEALTH AND HUMAN SERVICES National Institutes of Health National Cancer Institute, p. 19

Oral mucositis causes significant pain, interferes with eating, talking and swallowing, significantly diminishes enteral nutritional intake and has a substantial negative impact on quality of life (1, 6-10). Patients may require hospitalization for management of the complications of mucositis, including poor nutrition, dehydration and pain (1, 6-10). This becomes a significant burden on the patients, their families and the healthcare system alike. As well injury to the oral mucosa increases the risk of systemic infections (11, 12). Finally, the development of oral mucositis may require delays or dose reductions in future chemotherapy courses, potentially jeopardizing disease cure rates (6, 10).

Despite all that is known about the mechanism, course and complications of oral mucositis, there are no consensus guidelines on prevention or treatment of chemotherapy-induced oral mucositis and there is significant variation on approach to mucositis across treatment centers.

Caphosol (Jazz Pharmaceuticals, Inc. Palo Alto, CA) is a supersaturated aqueous electrolyte solution comprised of sodium phosphate, calcium chloride and sodium chloride, resembling human saliva that was designed in part to replace the normal ionic and pH balance of the oral cavity and been used to prevent and/or treat oral mucositis. Caphosol is hypothesized to diffuse into epithelial intracellular spaces and permeate mucosal lesions in oral mucositis. In addition, calcium may modulate the inflammatory response and tissue repair processes and phosphate may be involved in repairing damage to the mucosal surface. In a 2013 review article by Quinn et al., 24 of the 30 studies reviewed found Caphosol to be beneficial for the prevention and treatment of oral mucositis in patients receiving high-dose chemotherapy and/or radiotherapy (13). The author concluded that despite the heterogeneous nature of the reviewed studies, with many involving small patient numbers, involving single-centers and including historical controls, the data supported strong consideration for the addition of Caphosol to oral mucositis prevention and treatment plans. The largest, randomized study of Caphosol for the prevention and treatment of oral mucositis was a double blind adult study comparing Caphosol to fluoride therapy in 95 allogeneic and autologous hematopoietic stem cell transplant recipients (14). This 2003 study by Papas and colleagues, they reported that 40% of patients in the Caphosol arm had no mucositis compared with 19% in the control arm. Also, patients in the Caphosol arm had significantly fewer mean days of mucositis (3.72 vs. 7.22; $p=0.001$), duration of pain (2.86 vs. 7.67; $p=0.0001$), days receiving morphine (1.26 vs. 4.02; $p=0.0001$), dose of morphine (34.54 mg vs. 122.78 mg; $p=0.0001$) and days to the onset of neutrophil recovery $>200 \text{ mm}^3$ (11.12 vs. 12.56; $p=0.00173$) (14).

Although a 2014 randomized, controlled trial in 33 pediatric patients receiving high-dose chemotherapy failed to show any therapeutic benefit of Caphosol when initiated at development of mucositis, it did demonstrate safety of Caphosol therapy with no reported side effects (15). This study did not evaluate Caphosol for the prevention of oral mucositis which is the intention of our study. A prevention strategy for development of mucositis was chosen for this study objective as it would potentially allow for less analgesic to be used, less parenteral nutrition and shorter hospital stays compared to a treatment strategy when mucositis has already developed as attempts to enhance recovery of mucositis, particularly in the setting of profound neutropenia, would be more difficult given Caphosol's mechanism of action.

2.0 STUDY OVERVIEW

Eligible patients will be identified in the oncology clinic and/or the oncology ward and consented/enrolled on study. Study patients randomized to the Caphosol arm will begin Caphosol therapy prior to administration of systemic chemotherapy on Day 1 according to protocol. Caphosol administration will continue through the planned chemotherapy administration and until stopping criteria are met. Chemotherapy will be administered either in the MACC Fund Center or the inpatient service. Once the chemotherapy is complete the patient will be discharged to home and followed in the MACC Fund Center at regular intervals as dictated by standards of care. Caphosol treatment will continue at home as outlined in the protocol for 7 days following completion of chemotherapy and adequate neutrophil recovery, or until oral mucositis symptoms resolve, whichever occurs later. In the event the patient requires hospital admission, Caphosol treatment will continue according to protocol. The patient/family will keep a daily drug diary of administration of Caphosol throughout each cycle which will be reviewed by the study team at

each study visit. As well patients in each cohort will record in their diary other oral topical agents they are using and any narcotic and non-narcotic medications used for treatment of pain/mucositis.

2.1 Study Design

This is a randomized controlled trial designed for the purpose of evaluating the efficacy and tolerability of Caphosol therapy for the prevention of oral mucositis (Grade ≥ 2) in children, adolescents and young adults at risk for developing oral mucositis due to their cancer therapy.

Our hypothesis is that by initiating Caphosol at the initiation of chemotherapy administration, we will decrease the incidence and/or severity of oral mucositis (Grade 3 or 4) as well as limit the number of days requiring narcotic analgesics, days of hospitalization and need/duration of total parental nutrition in patients randomized to the treatment group compared to the control group.

Primary Objectives

- To determine if topically administered Caphosol at the initiation of chemotherapy prevents the development of oral mucositis (Grade ≥ 2) in children, adolescents and young adults.
- To determine the tolerability of four times daily Caphosol therapy.

Secondary Objectives

To determine if topically administered Caphosol reduces the severity of oral mucositis, as measured by incidence of severe mucositis (CTCAE v4.0 Grades 3 or 4), age-appropriate pain scores, use of narcotic pain medicine, number of hospital days and number of days on TPN.

3.0 SELECTION OF PATIENTS

Study patients will be recruited from the MACC Fund Center and the oncology inpatient service. Study entry is open to patients regardless of gender or ethnic background. While there will be every effort to seek out and include females and minority patients, the patient population is expected to be no different than that of other oncology studies at the Medical College of Wisconsin.

3.1 Inclusion Criteria

Oncology patients, at initiation of their oncology therapy, who are at risk of developing oral mucositis during their scheduled cancer therapy, defined by meeting one or more of the following criteria:

- a. Patients receiving one or more of the following chemotherapy agents:
 - Actinomycin D

- Carboplatin
 - Cisplatin
 - Cytarabine at doses ≥ 1 gram/m²
 - Daunorubicin
 - Doxorubicin
 - Methotrexate at doses ≥ 1 gram/m²
 - Mitoxantrone
- b. Age 0 to 25 years
- c. Voluntary written consent before performance of any study-related procedure not part of normal medical care, with the understanding that consent may be withdrawn by the subject at any time without prejudice to future medical care

3.2 Exclusion Criteria

- a. Patients receiving glutamine treatment for oral mucositis.
- b. Patients undergoing autologous or allogeneic hematopoietic cell transplantation are excluded from this study.
- c. Patients receiving concurrent Head & Neck radiation therapy or within 6 weeks of completion of radiation therapy.
- d. Pregnant or lactating patients. The agent used in this study is not known to be teratogenic to a fetus, but has not been studied, and there is no information on the excretion of the agent into breast milk. All females of childbearing potential must have a blood test or urine study within 2 weeks prior to registration to rule out pregnancy.
- e. Known allergy to Caphosol

4.0 REGISTRATION PROCEDURES

Registration will occur after eligibility is confirmed and the patient/parent has signed the subject consent, but before any treatment has been administered.

The eligibility checklist will be completed at the time of study enrollment.

4.1 Registration

Upon completion of the screening evaluation, eligibility confirmation and obtaining written consent, the patient will be registered in the study file by the Department of Pediatrics Division of Hematology/Oncology/BMT MACC Fund Center Clinical Trials Office (CTO). When the OnCore™ Clinical Trials Management System (CTMS) is fully functioning for this study, the MACC Fund Center CTO will use this program for patient registration.

4.2 Patients Who Do Not Begin Study Treatment

If a patient is registered on the study, and is later found not able to begin the planned study treatment, for whatever reason, the patient will be removed from study and treated at the physician's discretion. Study data will be collected until the time of study removal. The reason for removal from study will be clearly indicated on the case report forms.

If a patient begins treatment, and then decides to come off of study for whatever reason, the patient must be followed per Section 6.1.

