5.0 TREATMENT PLAN

This study is a randomized, controlled trial evaluating the use of topical Caphosol therapy to prevent oral mucositis (Grade ≥ 2) in children, adolescents and young adults undergoing chemotherapy. At the time of enrollment, patients will be randomized to either the control arm or the Caphosol arm. The treatment period will extend from the start of chemotherapy and continue for 7 days after completion of chemotherapy AND until the ANC is > 500 after nadir (count recovery) or until the symptoms of oral mucositis resolve; whichever occurs last.

Treatment

Caphosol Arm: Subjects randomized to the **Caphosol Arm** will use Caphosol 4 times per day as follows:

- Each dose consists of two 15 mL syringes, to be mixed at time of administration. Caphosol must be used within 15 minutes of mixing.
 - Subjects may increase the use to 6 times per day if they have symptoms of mucositis.
- Using one of the syringes, rinse and gargle (if patient is able) for one minute and then spit. Repeat using the remaining syringe.
 - For younger patients (less than or equal to 6 years of age), volume may be reduced to two syringes containing 5-10 mL each.
 - For patients unable to successfully rinse and spit, caregivers may paint their mouth (using medical sponge swabs) with the solution two times. Prior to swabbing the patient's mouth, squirt one of the syringes into a cup and using the medical sponge, soak up the solution and use the swab to coat the inside of the patient's mouth. Repeat using the second syringe.
- Patients are to avoid other oral medications, other mouth cares and food or drink for 15 minutes after using Caphosol.

- Patients will also use Biotene (5-10 mL) to swish and spit after the 15 minutes has passed. Biotene is part of our standard of care to prevent oral infections in oncology patients.

Control Arm: Subjects randomized to the **Control Arm** will use Biotene only 4 times per day as follows:

- Use 5 to 10 mL of Biotene to swish and spit
 - For patients unable to successfully rinse and spit, caregivers may paint their mouth (using medical sponge swabs) with the solution two times. Prior to swabbing the patient's mouth, pour Biotene into a cup and using the medical sponge, soak up the solution and use the swab to coat the inside of the patient's mouth. Repeat with a second swab.

The following will be observed:

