5.5 Follow-Up

Study patients will be followed through their first clinic appointment after treatment completion with the appropriate evaluations. Data collection will continue through completion of planned therapy, or until subject meets criteria for removal from protocol therapy or off –study criteria are met as outlined below. Patients who are removed from study per the protocol criteria below, or who withdraw from the study, will not be replaced but will be treated as part of the analysis using either an “intention to treat”, “last observation carried forward” or “by imputation of the missing values”.

Study evaluations will occur each time chemotherapy is received where Caphosol is administered.

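### Section 4.2 ends data collection for randomised patients who cannot begin study treatment, so their primary outcome is not observed, and it is not reconciled with 5.5 or 5.6.2

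*Combined protocol and SAP*

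**What the plan says.** Registration follows consent and confirmation of eligibility "but before any treatment has been administered" (Section 4.0). Section 5.0 states: "At the time of enrollment, patients will be randomized to either the control arm or the Caphosol arm"; Table 1 in Section 5.1 agrees. Section 2.0 fixes the start of the rinse: "Study patients randomized to the Caphosol arm will begin Caphosol therapy prior to administration of systemic chemotherapy on Day 1". Allocation therefore precedes the first rinse.

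The first paragraph of Section 4.2 deals with a registered patient later "found not able to begin the planned study treatment, for whatever reason, the patient will be removed from study". It adds: "Study data will be collected until the time of study removal". The second paragraph treats those who start differently: "If a patient begins treatment, and then decides to come off of study for whatever reason, the patient must be followed per Section 6.1". No Section 6.1 exists; Section 6.0 is a calendar without subsections.

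Section 5.5 says that patients removed under the criteria that follow it, or who withdraw, "will not be replaced but will be treated as part of the analysis", by intention to treat, last observation carried forward (LOCF) or imputation, with no choice among the three. It also lets data collection end when a patient meets the criteria for removal from protocol therapy. Section 5.6.2 lists three off-study reasons: death, loss to follow-up, and withdrawal of consent for further data. Failure to start is not among them.

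Both arms use a Biotene rinse, and Section 5.0 explains: "Biotene is part of our standard of care to prevent oral infections in oncology patients". Caphosol is the only added product.

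**The concern.** The primary outcome is mucositis of Grade 2 or worse during the chemotherapy period. A patient removed under 4.2 before the first rinse has at most a pre-study grade, even if the same chemotherapy is then given at the same centre. The plan thus discards the outcome of a patient it has already randomised, for a reason that arises after allocation.

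Two things are at stake. The comparison may cease to be the randomised one, if non-starters differ from other patients in mucositis risk and are unevenly spread between the arms. And the site lacks a consistent instruction: 4.2 ends data collection for non-starters, 5.5 keeps removed patients in the analysis without mentioning 4.2, and 5.6.2 does not count not starting as a reason to leave the study.

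**Working it through.** **The plan's own figure.** Section 10.3 gives 48 per group for a 30-point difference, alpha 0.05, power 80%, without arm rates or sidedness. Assume 55% versus 25% and a two-sided test. The mean rate is 0.40, and n = [1.96·√(2·0.40·0.60) + 0.842·√(0.55·0.45 + 0.25·0.75)]² / 0.30² = (1.358 + 0.555)² / 0.09 = 40.7, so 41; with continuity correction it is 48. Fisher's exact test at 48 per arm then has 80.8% power. The figure is reproducible, and this point does not dispute it. It serves as the denominator below.

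**Inputs.** From the documents: 48 per arm (10.3), and an incidence of around 40% with myelosuppressive chemotherapy for solid tumours (Section 1.0, no grade stated). Assumed, because the documents are silent: the number of Caphosol non-starters k, their risk r, and no control non-starters.

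**Step 1: information lost.** With k outcomes missing, the arm's incidence among all randomised patients is undetermined over a width of k/48.
- k = 1: 1/48 = 2.1 points
- k = 2: 2/48 = 4.2 points
- k = 5: 5/48 = 10.4 points

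This needs no assumption about risk.

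**Step 2: bias if non-starters are dropped and there is no true effect.** Observed Caphosol rate = (0.40·48 − k·r)/(48 − k), against 40% in control.

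| k | r | Observed Caphosol rate | Spurious difference |
|---|---|---|---|
| 2 | 60% | 18.0/46 = 39.1% | 0.9 points for Caphosol |
| 4 | 75% | 16.2/44 = 36.8% | 3.2 points for Caphosol |
| 5 | 80% | 15.2/43 = 35.3% | 4.7 points for Caphosol |
| any | 40% | 40.0% | none |
| 4 | 20% | 18.4/44 = 41.8% | 1.8 points against Caphosol |

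A second baseline, 50% in both arms with k = 5 and r from 70% to 90%, gives (24 − 3.5)/43 = 47.7% down to (24 − 4.5)/43 = 45.3%, a spurious benefit of 2.3 to 4.7 points. The chance of a false finding for Caphosol then rises from 2.5% to about 4.1% to 6.4%.

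**Step 3: price of keeping them.** Take 55% versus 25%, with non-starters at the control rate. The Caphosol rate becomes (0.25·46 + 0.55·2)/48 = 26.3% for k = 2, or (0.25·43 + 0.55·5)/48 = 28.1% for k = 5. The 30-point difference shrinks to 28.8 or 26.9 points. Power without continuity correction goes from 86.3% to 82.9% or 77.0%.

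**The case against.** A reader might infer that the removals fall almost wholly on the Caphosol arm. The documents do not support that. Section 4.2 names no arm, Biotene four times daily is also protocol-assigned, and cancelled or changed chemotherapy can occur in either arm. Nor is inability to rinse the same as inability to begin: swab application is allowed in both arms, and smaller Caphosol volumes are allowed for young children. What stands is plausibility: Caphosol is the only addition to standard care, no blinding is described, and refusal or supply failure specific to Caphosol can arise only in that arm.

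A reader might also infer that intention to treat becomes impossible. Section 5.5 offers imputation, so non-starters could stay in the denominator with imputed outcomes or best- and worst-case bounds. That is feasible, but it rests on assumption, and LOCF would carry forward only the pre-study grade.

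Section 5.6.1 lists refusal as removal from protocol therapy, so a patient who refuses, rather than one who is unable to begin, may fall outside 4.2. And 5.5 refers to the criteria in 5.6, not to 4.2, so the conflict is a gap left unreconciled more than a direct contradiction. Both are fair. They show that the text leaves the handling of such patients open.

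Finally, the counts and risks above have no source in the documents, and even 4.7 points is small beside a 30-point design difference. That is correct, and it limits the size of the claim.

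**Conclusion.** The point holds in this form: followed as written, 4.2 leaves randomised patients without an observed primary outcome, and it is not reconciled with 5.5 or 5.6.2. The firm figure is 2.1 points of undetermined incidence per missing Caphosol patient. The spurious benefit of 0.9 to 4.7 points is an illustration. It assumes no true effect, 40% incidence, 2 to 5 non-starters in the Caphosol arm only, and risks of 60% to 80%. The bias is nil at average risk, reverses at lower risk, and is absent if everyone starts. Neither a bias certain to favour Caphosol nor a loss confined to that arm can be read from the documents. The change is still worth making, because on-treatment grades that are not collected at the time cannot be reliably recovered.

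**What to change.** Rewrite the first paragraph of 4.2 so that a randomised patient who receives the listed chemotherapy but does not begin the assigned rinse stays on study. Mucositis grade, pain score, narcotic use, hospital days and TPN are then collected on the Table 2 schedule, and the patient is analysed in the assigned arm. Only the 5.6.2 reasons end data collection. Patients whose listed chemotherapy is never given may be excluded, by the same rule in both arms.

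Amend 5.5 to match: state that it covers 4.2 patients, and that removal from protocol therapy does not end outcome collection. Correct the reference to Section 6.1 at the same time.

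The cost is text in two sections and a few more patients graded at visits they attend anyway. No treatment decision changes. The estimated effect is somewhat diluted by non-starters, as an intention-to-treat comparison should reflect. On the assumptions above, power falls by 3.4 points with 2 non-starters (86.3% to 82.9%) and by 9.3 points with 5 (86.3% to 77.0%).
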